## **I. Measurement methods**

### *Setting*

The subjects involved in the research will be analyzed at the LAMBDA laboratory (UDGEE), AUSL-IRCCS of Reggio Emilia.

### *Tools*

The elective methodology for this type of investigation is the electromyographic analysis, which allows to highlight the timing of muscle activation and therefore the motor coordination that underlies the balance. Surface electromyography will be used, which is neither painful nor invasive.

The detection system is able to acquire up to 16 channels with a sampling frequency of 1000Hz. Each channel corresponds to a device capable of pre-filtering and amplifying the signal, before transmitting it via wireless to the PC dedicated to the acquisition of the signal itself. Each of these devices is placed on a muscle. The connection with the skin takes place via two adhesive electrodes in Ag-AgCl, equipped with conductive gel (they are the same used for the electrocardiogram). The electrodes measure a potential difference, recording the surface current generated by muscle contraction (as does the ECG for the heart).

During the measurement, other parameters are monitored by:

- force platforms: two AMTI® platforms capable of detecting the center of pressure (COP), the direction and the intensity of the resultant of the forces applied on them with a frequency of 1000Hz;
- optoelectronic system: Vicon® system (Oxford Metrics Group, UK) with 7 infrared cameras capable of detecting the position in space of reflective markers with an accuracy of 1mm (for the identification of the 3D position of a marker it is necessary that it is visible for at least two cameras at the same time; each camera

is equipped with a crown of infrared LEDs to increase the visibility of the markers without disturbing the acquired subjects; the sampling frequency is 100Hz, sufficient to accurately detect the body kinematics;

- video cameras: two video cameras with perpendicular axes that acquire at 100Hz and allow you to immediately provide an overview.

Thanks to these systems it is possible to monitor the movement of the COP with respect to the foot in support (it allows to visualize the medial and lateral imbalance), and to evaluate the loads and movements of the various body segments (the motor strategies for maintaining balance are displayed).

### *Measurement protocol*

The analysis will be carried out on the right lower limb of each subject.

The electromyographic devices will be applied to the tibialis anterior, peroneus longus, gluteus medius, gluteus maximus and adductor longus.

The reflective markers will then be applied (using double-sided tape) according to the Total3DGait protocol, which identifies the body segments of the forearms, arms, trunk, pelvis, thighs, legs, and feet.

The subject must position himself with his right foot on a force platform.

The toe of the left foot will be allowed to rest on the ground (on the other power platform placed at the rear), with the verbal indication to load as little weight as possible on it: this indication is aimed at reducing muscle activation in the absence of external perturbations, in order to highlight only the activity caused by the perturbations themselves. Only acquisitions in which the load on the left foot will be less than 30% of the weight will be considered valid.

The hands will be placed on the hips to limit the variables to be controlled and to standardize the posture, in order to focus the contribution to the balance of the lower limb. The left thigh has to be kept vertical. Finally, it will be required to find, within the constraints described above, the posture that is as comfortable as possible, with minimal muscle contraction. The distance between the feet is therefore freely chosen by each subject.

The operator positions himself behind the subject to be examined, and without being seen performs lateral thrusts with the medial margin of the hand at the proximal third of the thigh. At least ten pushes per side will be performed, with random timing. The thrusts will be quick but without causing pain.

The operator will then request maximal contractions from the subject, in order to normalize the electrical activity of each muscle with respect to its maximum. It will be required to perform the dorsiflexion and pronation of the foot against resistance, then the adduction, abduction and extension of the hip.

The whole procedure takes about an hour.

### *Data processing*

Electromyographic signals are processed in the following way:

- high pass filter: to eliminate any disturbances (movement artifacts) and keep only the high frequency signal typical of muscle activity;
- rectification: the signal, which is an oscillation around zero, is taken only as an absolute value;
- envelope: application of the Root Mean Square on a span of 200ms (before and after) and moving average, to quantify the extent of muscle activation;

- normalization: muscle activation is normalized with respect to the maximum contraction value; it is therefore expressed as a percentage of this value;
- median: for each muscle of each subject the median of the different response activations is calculated; the median, once a series of values has been placed in ascending order, is constituted by the central value; compared to the average, it allows to reduce the influence on the final value of the most anomalous cases compared to the majority;
- correlation coefficient: calculation of the correlation coefficient to verify any synergies present between the different muscle groups.

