#### **H. Outcome measures**

The core of the study consists in carrying out a measurement of activation of the muscles of the lower limb. In particular, it will be necessary to measure this activation as a response to an imbalance / perturbation in monopodal stance.

Muscle activity will be evaluated for 1500ms, 500ms before and 1000ms after the disturbance. The early response to the stimulus will be identified in the interval of 100-500ms after the stimulus.

The muscles considered will be, for the anterior spiral chain, the adductor longus and the peroneus longus, for the posterior spiral chain, the glutei (medium and large) and the tibialis anterior. Therefore, both muscles of the thigh (glutei and adductor longus) and of the leg (peroneus longus and tibialis anterior) will be examined.

The goal is to understand which of these muscles are activated together, in particular if the muscles belonging to the same myofascial chain are activated together. The simultaneous activation will be measured with the calculation of the correlation coefficient. The hypothesis of spiral chains use for the balance will be

considered reasonable if it is possible to observe greater correlation between the peroneus longus-adductor longus and between the glutei-tibialis anterior than the correlation between the glutei-peroneus longus and between the tibialis anterior- adductor longus.

The outcome measures will therefore be:

- Maximum intensities of early activation, normalized with respect to the electrical intensity measured in the maximal contraction, respectively in response to a stimulus that causes a medial and lateral imbalance;
- Correlation coefficients between the electrical activities of:
  - adductor longus-peroneus longus
  - glutei-tibialis anterior
  - glutei-peroneus longus
  - adductor longus-anterior tibialis

in response to a stimulus that causes medial imbalance;

- Correlation coefficients between the electrical activities of:
  - adductor longus-peroneus longus
  - glutei-tibialis anterior
  - glutei-peroneus longus
  - adductor longus-anterior tibialis

in response to a stimulus that causes lateral imbalance.

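### Must the plan state what the muscle correlation coefficient runs over before its chain comparison can be used?

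*Combined protocol and SAP*

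**What the plan says.** Section H (Outcome measures) contains the plan's only decision rule. The hypothesis is to be "considered reasonable if it is possible to observe greater correlation between the peroneus longus-adductor longus" pair, and between the glutei and tibialis anterior, than between the two cross-chain pairs. The coefficients are listed separately for medial and lateral imbalance.

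On what the coefficient stands for, Section H says: "The simultaneous activation will be measured with the calculation of the correlation coefficient". It gives two time windows: "Muscle activity will be evaluated for 1500ms, 500ms before and 1000ms after the disturbance", and "The early response to the stimulus will be identified in the interval of 100-500ms after the stimulus". Only the maximum-intensity outcome refers to the early response; the correlation outcomes mention no window.

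The Data processing list in Section I runs from filter to envelope ("application of the Root Mean Square on a span of 200ms (before and after) and moving average"), normalisation and median ("for each muscle of each subject the median of the different response activations is calculated"), and ends with "calculation of the correlation coefficient to verify any synergies present between the different muscle groups". Under Measurement protocol, "At least ten pushes per side will be performed, with random timing". Section K seeks an indicative trend in five subjects and rules out any calculation of statistical significance.

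**The concern.** A correlation needs a unit, and the recordings offer three: time samples within a response, pushes within a subject, or subjects. The plan names none, and ties neither window to the coefficient. Because the correlation step follows the median step, a literal reader could take the medians as its input. If those medians are curves, the push-by-push pairing of muscles is lost. If they are single values, each coefficient rests on five points, one per subject.

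Two analysts could therefore compute different coefficients from the same recordings and disagree on whether the hypothesis is reasonable. Section E also says the results may feed the definition of an optimal method for later work, which an undefined index would serve poorly.

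**Working it through.** The plan states no power, alpha or calculated sample size, so there is no figure to reproduce. The check takes the possible readings in turn.

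**1. Points per coefficient, one direction.** At 1000 Hz (Section I, Tools) the full window gives 500 + 1000 = 1500 samples and the early window 500 - 100 = 400. There are at least 10 pushes per subject, and 5 subjects (Section G).

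**2. Subjects as the unit.** Five single values per muscle cannot show that muscles fire at the same moment, so this reading conflicts with the purpose stated in Section H. It would also be nearly uninformative. The Fisher interval is tanh(atanh(r) ± 1.96/√(n - 3)). For r = 0.5 and n = 5 this is tanh(0.549 ± 1.386) = -0.68 to 0.96. A sensible analyst would not choose it.

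**3. Time as the unit: within each push, or on the median curve.** Simulation under assumptions not in the documents: Gaussian EMG with gamma-shaped bursts, glutei as one signal, 10 pushes, Pearson r, RMS half-width 100 or 200 ms, window 100-500 ms, own latency jitter SD 10 ms except where varied in the no-effect runs, 400 simulated subjects per cell (Monte Carlo standard error at most √(0.25/400) = 2.5 points). Entries are the share of subjects whose mean same-chain r exceeds mean cross-chain r (chance 50%). Brackets give the share with both same-chain values above both cross-chain values (chance 1/C(4,2) = 1/6 = 16.7% if the four are exchangeable).

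| Assumed truth | Median curve | Median of within-push r |
|---|---|---|
| Chains 30-100 ms apart | 89-100% [50-100%] | 92-100% [44-100%] |
| Only one chain responds | 94-96% [30-33%] | 98-99% [26-32%] |
| Shared gain, same timing | 47-52% [10-14%] | 52-54% [11-13%] |
| No chain effect | 50-56% [10-13%] | 50-54% [12-16%] |
| Latencies shift together in a chain (SD 30-50 ms) | 58-68% [14-25%] | 96-100% [72-96%] |

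The first four rows are close. The last depends on the assumed ratio of shared to own latency variation. In further runs (200 subjects per cell), shared 20 ms with own 20 ms gave 49-57% against 74-80%. Shared 10 ms with own 20 ms gave 44-55% against 55-64%.

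**4. Window.** With chains 100 ms apart, mean cross-chain r is 0.09-0.15 over 100-500 ms and 0.70-0.84 over 1500 ms. The rule asks only which coefficients are greater. In the further runs the mean comparison held in 100% of subjects over both windows. In the shared-latency row, 1500 ms gives 58-75% against 96-100%, the same contrast as above.

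**5. Pushes as the unit.** A second simulation (200 runs of 5 subjects and 10 pushes; push-to-push log amplitude correlated 0.5 within a chain; strict rule) met the rule in 92% of runs with peaks correlated across pushes. It was met in 13.5% over time samples in the full window, 14% in the early window, and 21% across subjects. With no chain link the range was 11-25%. This contrast is large, but it separates two constructs: co-variation in size and coincidence in time. With chains 100 ms apart the peak coefficient is at chance (45-52%), while both time-based versions reach 100%.

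**The case for a change.** The strongest case for a change is that this comparison is the plan's whole verdict, that the unit can alter it (92% against 14% in step 5), and that a few lines would settle it with no new measurement. Fixing the definition before data are seen would also prevent choosing whichever coefficient favours the hypothesis. The absence of significance testing does not answer this, since the plan still applies a rule.

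Much of that stands. The definition is missing, the timing and amplitude readings can disagree, and within-push pairing is better when latencies move together. Three things weaken the step from there to a required change.

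- The text does not show that the medians feed the correlation. They may serve the maximum-intensity outcome alone, so no stated rule is shown to be wrong.
- The obvious remedy, the median of within-push coefficients, is itself a choice of construct. It misses shared gain (52-54%, against 94-96% for peaks across pushes). It is also noisy in the early window, which spans only one to two envelope lengths (400/400 to 400/200). For unrelated muscles the per-push r has SD 0.47-0.49, and the median over 10 pushes has SD 0.21.
- That remedy would not make the rule unique. Coefficient type, the forming of one glutei signal from two channels, mean or strict comparison, and the combining of directions would remain open.

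**Conclusion.** No change to the plan follows. The missing detail is real, but Section H's stated purpose leads a sensible analyst to correlation over time, with 1500 ms as the general evaluation period. Between the two time-based versions, results are similar in four of five scenario groups. In the fifth, the advantage of within-push pairing ranges from large (96-100% against 58-68%) to small (55-64% against 44-55%), depending on latency ratios that the documents do not give. The window is not shown to change the ordering.

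The one large divergence, between timing and shared amplitude, is a choice of construct for the sponsor. In a five-subject feasibility study that seeks an indicative trend and is meant to inform later methodology, leaving it to the analysts is acceptable, provided the report states which coefficient was used. All percentages rest on assumed waveforms and variances. They show sensitivity to the choice and do not predict this study's results.

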#### **J. Duration of the study**

Total expected duration: 6 months

Enrollment: 1 month

Measurements: 2 months

Data processing: 3 months

#### **K. Statistical aspects**

As this is a preliminary study, a sample size such as to provide statistical significance is not sought. The sample must be functional to test the method and to verify if in the subjects considered it is possible to detect an (indicative) trend that is consistent with the hypothesized motor strategy. For this reason, the number of 5 subjects was considered suitable and no parameters to be considered statistically significant will be calculated.

#### **L. Data management (privacy)**

Acquisition data are automatically stored on the laboratory's dedicated PC.

The data of each subject are recorded with an identification number, without reference to personal data of the subject.

Access to the PC is password protected, and the PC is not connected to the internet.

Data processing is carried out directly on the PC itself, so no data transfers must take place.

The CRF forms for data collection will be in paper format.

#### **M. Authorization aspects**

It is believed that the study does not present critical issues from an ethical point of view, as measurements are carried out with methods used in ordinary clinical activity and which are non-invasive, non-dangerous, short-term and on healthy subjects.

The consent to the study will be signed before the measurements are taken, after a detailed explanation provided to each subject regarding the measurements themselves and the method of analysis.

No financial agreements are envisaged. The study is carried out as a consensual agreement between all the parties involved.

The AUSL-IRCCS di Reggio Emilia will process the personal data of the subjects participating in the trial as independent Data Controller, pursuant to and for the purposes of the European legislation referred to in GDPR 679/2016 and, as currently applicable, of Legislative Decree 196/2003 .

The AUSL-IRCCS di Reggio Emilia is the owner of the data collected in clinical practice and for the use of personal and sensitive data of patients for research purposes, the express consent of the interested party will be requested, as required by the aforementioned legislation, on the basis of documents approved by the competent Ethics Committee .

The data will be used solely for the purpose of carrying out this study.

The Scientific Responsible of the study is identified as the Delegate for the processing of personal data, pursuant to the Deliberation of the General Manager n. 284/2018, and will appoint with a specific written deed the other collaborators as persons authorized to process personal data under the authority of the owner and the data processing delegate, pursuant to GDPR 679/2016.

The study will be activated only after obtaining the favorable opinion of the Comitato Etico di Area Vasta Nord RER and will be carried out in accordance with this protocol, any amendments introduced and will be conducted in accordance with the ethical principles of the Declaration of Helsinki.

The data will be managed ensuring the protection of privacy in accordance with the provisions of the law (GDPR 679/2016).

The data necessary to respond to the objectives of the study will be recorded in coded form (in accordance with the GDPR 679/2016), therefore the processing of personal data will take place in such a way that the data can no longer be attributed to a specific data subject without the use of additional information, information that will be stored separately and will be subject to technical and organizational measures designed to ensure that it is not attributed to an identified or identifiable natural person. The data will be stored, whether in paper or electronic form, in places or media protected from access by unauthorized persons or intrusion by third parties.

The PI will file and keep in paper format in a protected place, the patient's personal data combined with the assigned ID, together with the signed and dated informed consents and the clinical documentation collected according to the methods of its center (reports, copy of the relevant parts of the medical record).

#### **N. Responsibility and publication policy**

The data collected will be the property of the promoter.

#### **O. Insurance aspects**

Since it is believed that the measurement setting is safe and that the measurements to be carried out do not present risks, as they are non-invasive and non-dangerous, the stipulation of a specific insurance is not considered necessary.

